9.3.3.4 DEFINITION OF UNEXPECETED ADVERSE EVENTS (SAE)

An adverse event will be considered "unexpected" if it is not listed in the investigator brochure or is not listed at the specificity or severity that has been observed; or, if it is not consistent with the risk information described in section 9.3.3.3 of this study protocol.

9.3.4 TIME PERIOD AND FREQUENCY FOR EVENT ASSESSMENT AND FOLLOW-UP

The occurrence of an adverse event (AE) or serious adverse event (SAE) may come to the attention of study personnel during study visits and interviews of a study participant presenting for medical care, or upon review by the study monitor (see section 11.1.7).

All AEs including local and systemic reactions not meeting the criteria for SAEs will be captured on the appropriate case report form (eCRF). Information to be collected includes event description, time of onset, clinician's assessment of severity, relationship to study drug (assessed only by those with the training and authority to make a diagnosis), and time of resolution/stabilization of the event. All AEs occurring while on study drug will be documented appropriately regardless of relationship. All AEs will be followed to adequate resolution.

Any medical condition that is present at the time that the participant is screened will be considered as baseline and not reported as an AE. However, if the study participant's condition deteriorates at any time during the study, it will be recorded as an AE.

Changes in the severity of an AE will be documented to allow an assessment of the duration of the event at each level of

severity to be performed. AEs characterized as intermittent require documentation of onset and duration of each episode.

The study coordinator will record all reportable events with start dates occurring any time after informed consent is obtained until 7 (for non-serious AEs) or 30 (for SAEs) days after the last day of study participation. At each study visit, the investigator will inquire about the occurrence of AE/SAEs since the last visit. Events will be followed for outcome information until resolution or stabilization.

9.3.5 ADVERSE EVENT REPORTING

We will report all serious AEs according to appropriate authority (e.g. IRB, NIAMS, FDA) in compliance with guidelines and regulations established by the Data Safety Monitoring Board. See **Appendix 9** Data Safety Monitoring Plan.

9.3.6 SERIOUS ADVERSE EVENT REPORTING

We will immediately report to the DSMB and any serious adverse event, whether or not considered study intervention related, including those listed in the protocol or investigator brochure and will include an assessment of whether in the view of the site PI there is a reasonable possibility that the study intervention caused the event. Study endpoints that are serious adverse events (e.g., all-cause mortality) will be reported in accordance with the protocol unless there is evidence suggesting a causal relationship between the study intervention and the event (e.g., death from anaphylaxis). In that case, the investigator will report the event to the NIAMS and DSMB via KAI within 48 hours of the investigator becoming aware of the event.

All serious adverse events (SAEs) will be followed until satisfactory resolution or until the site investigator deems the event to be chronic or the participant is stable. All SAEs , regardless of relatedness will be reported to the NIAMS and the DSMB via KAI within 48 hours of becoming aware of the event. Supporting documentation of the event will be provided by the DCC.

The Data Coordinating Center will be responsible for notifying the Institutional Review Board, Food and Drug Administration (FDA), NIAMS/KAI, and any other body as mandated by the DSMB of any unexpected fatal or lifethreatening suspected adverse reaction within 24 hours. In addition, the Data Coordinating Center will notify FDA and all participating investigators of any unexpected fatal or life-threatening suspected adverse reaction as soon as possible, but in no case later than 15 calendar days after it is determined that the information qualifies for reporting.

9.3.7 REPORTING EVENTS TO PARTICIPANTS

Participants will be informed about new AEs and SAEs, and on conclusion of the study, study-related results at an aggregate level.

9.3.8 EVENTS OF SPECIAL INTEREST

9.3.8.1 INFUSION REACTIONS (IRS)

As described in section 8.3.3.3 during pre-marketing controlled clinical trials, infusion reactions (IR) were reported in 26% of patients treated with pegloticase 8 mg every 2 weeks. IRs will be defined as any infusion-related AE or cluster of temporally-related AEs, not attributable to another cause, which occur during or within 2 hours after the infusion of

pegloticase. Other AEs that occur outside of the 2-hour window following the infusion may also be categorized as an IR per site PI discretion. Signs and symptoms of the IR, and treatments administered, will be documented in the medical record and in the eCRF. Examples of AEs not considered possible IRs include but are not limited to: laboratory abnormalities that are unlikely to have occurred during or within 2 hours following the infusion (e.g., anemia, hypercholesterolemia), gout flares, most infectious diseases, or the recurrence or worsening of a known chronic medical problem identified in the participant's medical history.

IRs are not uncommon when biological agents are administered by IV infusion. Therefore, all participants will receive pre-treatment prophylaxis consisting of at least an antihistamine and corticosteroid prior to each infusion of pegloticase (see **Table 2**). In order to standardize this regimen, participants will take fexofenadine (60 mg, PO) the night before and again on the morning of the infusion with acetaminophen (1000 mg, PO) Prior to the infusion, hydrocortisone (200 mg, IV) will be administered and a at minimum, a targeted physical exam will be performed. The name, dose, route, date, and time of administration of each prophylactic medication will be recorded in the medical record and in the CRF.

Table 2. Infusion Reaction Prophylaxis

Night Before Infusion	Morning of Infusion	Following Arrival at Infusion Clinic
Participant takes:	Participant takes:	Abbreviated physical examination to include:
Fexofenadine (60 mg) PO	Fexofenadine (60 mg) PO	Dermatological – Noting Any Rashes
	Acetaminophen (1000 mg) PO	Chest – Noting Breath Sounds
		Vital Signs
		Start IV and Administer hydrocortisone (200 mg)
		Initiate Drug Infusion

9.3.8.2 PREGNANCY

Premenopausal women will have a pregnancy test before the study starts and again throughout the study. If participants suspect that they may have become pregnant during the study, the study coordinator will contact the study PI immediately and the PI or Study Coordinator will instruct the participant to stop taking all study medication. If it is confirmed that the participant is pregnant, they will be withdrawn from the study. The study PI will schedule a follow-up visit and may choose to follow the outcome of the pregnancy. If it is discovered that participants are breastfeeding, they are not eligible to participate in the study and their participation will be discontinued immediately.

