- o In rare cases in conditions (e.g. transplant, Systemic Lupus Erythematosus (SLE)) other than gout mycophenolate mofetil has been linked (incidence rate of 14.4 cases/100,000 person-years and 289/100,000 person-years respectfully) with a serious disorder of the brain known as Progressive Multifocal Leukoencephalopathy (PML). Following discontinuation of MMF patient conditions typically improve with marked reduction of weakness, and in follow-up MRI showed regression of lesions over the next 6 months. We will actively monitor participants and in the event of suspected diagnosis of PML, MMF will be withdrawn.
- Mycophenolate mofetil use is associated with increased risks of pregnancy loss and congenital malformations.

b. Pegloticase (Infusion)

i. Immediate Risks

It is common for potent urate lowering therapies to lead to acute attacks of gout. Other uncommon symptoms reported in at least 5% patients treated with pegloticase that may occur during the study period are ecchymoses, sore throat, constipation, chest pain, and vomiting. Serious allergic reactions may happen in some people while receiving infusion of pegloticase. These infusion reactions can be serious and usually happen within 2 hours of the infusion. Chest discomfort (15%), flushing (12%), and dyspnea (11%) are the most common symptoms. Symptoms associated with pegloticase infusion resolve with slowing, interrupting, or stopping the infusion. 91% of these symptoms occur in patients with serum urate concentrations greater than 6 mg/dL. Therefore, all participants serum urate will be checked prior to infusion and any participant with 2 or more serum urate test > 6 mg/dL (following initial infusion) will not be infused and will be removed from the study. Symptoms associated with infusion reactions include:

- Hemolysis; Individuals with G6PD deficiency are excluded from the study
- O Join pain 14%; Pain following injection. Pain subsides over time
- o Difficulty breathing 14%; Subsides over time
- Muscle spasms 14%; Subsides over time
- o Nausea 9%; Subsides over time
- Fever 14%; Subsides over time
- Back pain 14%; Subsides over time
- Diarrhea 14%; Subsides over time
- Erythema 14%; Subsides over time
- Hypersensitivity 14%; Subsides over time
- Rash 29%; Subsides over time
- Pain/bruising at the infusion site; Pain following injection and bruising will subside over time.

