9.3.2 DEFINITION OF SERIOUS ADVERSE EVENTS (SAE)

A SAE is any AE occurring at any dose that results in any of the following outcomes:

- Death
- Is life-threatening (places the participant, in the view of the site PI, at immediate risk of death from the AE as it occurred)
- Inpatient hospitalization or prolongation of existing hospitalization (hospitalization is defined as an inpatient admission, regardless of length of stay, even if hospitalized as a precautionary measure for continued observation)
- A permanent, persistent, or significant disability (substantial disruption of the ability to conduct normal life

functions). A medically significant AE that may jeopardize the participant and may require medical or surgical intervention to prevent one of the outcomes listed in this definition

Events NOT considered to be **Serious** are:

- Hospitalization for treatment, which was elective or pre-planned, for a pre-existing condition that did not worsen
- Treatment on an emergency, outpatient basis for an event NOT fulfilling any of the definitions of serious given above and NOT resulting in hospital admission
- An event that, had it occurred in a more serious form, might have caused death
- A sign, symptom, or event that is noticeable but easily tolerated.
- An event does not significantly influence performance or prevent the participant from carrying on with their usuall life activities.

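### Congenital malformation is a named MMF risk, but it is not an SAE criterion and pregnancy follow-up is optional, so a malformation could go unrecorded

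*Combined protocol and SAP*

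**What the plan says.** - **The risk (section 3.3.1).** Among the longer-range risks the protocol states: "Mycophenolate mofetil use is associated with increased risks of pregnancy loss and congenital malformations".
- **The SAE definition (section 9.3.2).** It opens "A SAE is any AE occurring at any dose that results in any of the following outcomes" and then lists death, life-threatening events, hospitalization, disability and a general item: "A medically significant AE that may jeopardize the participant and may require medical or surgical intervention". Congenital anomaly or birth defect is not listed.
- **Pregnancy (section 9.3.8.2, under events of special interest).** "If it is confirmed that the participant is pregnant, they will be withdrawn from the study". The PI then schedules one follow-up visit and "may choose to follow the outcome of the pregnancy".
- **Recording window (section 9.3.4).** Events are recorded if they start after consent and "until 7 (for non-serious AEs) or 30 (for SAEs) days after the last day of study participation". The section adds that events are followed until they resolve or stabilize.
- **Follow-up after stopping.** Section 8.1 and the reminder under Visit 17 in section 9 ask for visit 17 and then the three monthly visits 18 to 20. The Follow-up paragraph in section 9 keeps a participant who stops study drug on the full schedule, which ends at week 36.
- **Use of the data.** Section 4 makes the incidence and type of AEs and SAEs a co-primary endpoint.

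**The concern.** A harm that the protocol itself attributes to MMF has no dependable route into the safety data. Three provisions act together. The definition does not call a malformation serious. The pregnancy section does not require anyone to find out how the pregnancy ended. The recording window can close before birth. Staff could follow every one of these rules, commit no deviation, and still leave a malformation after MMF exposure out of the record.

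What is at stake is the completeness of a co-primary safety endpoint for a rare but irreversible harm, in a trial meant to inform whether this combination is studied further.

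**Working it through.** The plan states no figure on this point, so there is none to reproduce. The check has two parts.

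**1. Would a malformation meet the definitions?**

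- Section 9.3.1 defines an AE broadly, as an untoward medical occurrence. A malformation that came to light could be recorded as an AE.
- To be serious under section 9.3.2 it would have to involve death, threat to life, hospitalization, disability or the general item. The life-threatening and general items are worded for the participant, so they do not clearly reach a fetus or child. A malformation that leads to hospitalization or disability might be read into the list; one that does not has no criterion to meet.
- Either route depends on the outcome being learned, and section 9.3.8.2 leaves that to choice.
- Section 9.3.3.3, which lists expected MMF events, does not mention pregnancy loss or malformation and only refers back to the risk section.

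**2. Would the window still be open at birth?**

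Inputs from the protocol:
- SAE window: 30 days after last participation (9.3.4) = 30/7 = 4.3 weeks.
- Visit 17 two weeks after discontinuation (8.1), then three visits at 4-week intervals (section 9) = 2 + 12 weeks.
- Full schedule ends at week 36. MMF or placebo is taken from week -2 to week 12 (Table 1).

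Assumptions, not in the documents: birth 38 weeks after conception (range 36 to 40), and pregnancy detected about 4 weeks after conception.

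| Follow-up rule | Window closes | Compared with birth |
|---|---|---|
| (a) Withdrawn at detection (9.3.8.2), plus 30 days | 4 + 4.3 = 8.3 weeks after conception | 36 to 40 weeks: outside |
| (b) Visits 17 to 20 completed (8.1; section 9, Visit 17), plus 30 days | 4 + 2 + 12 + 4.3 = 22.3 weeks after conception | 36 to 40 weeks: outside |
| (c) Full schedule (section 9, Follow-up), plus 30 days | 36 + 4.3 = study week 40.3 | inside only for conceptions up to week 40.3 - 38 = 2.3 |

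Under (c) the latest conception covered ranges from 40.3 - 40 = week 0.3 to 40.3 - 36 = week 4.3. MMF exposure spans 12 - (-2) = 14 weeks. If conceptions were spread evenly over it, the uncovered share would be (12 - 2.3)/14 = 69%, with a range from (12 - 4.3)/14 = 55% to (12 - 0.3)/14 = 84%.

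The detection assumption does not drive (a) or (b). For a birth at 36 weeks to fall inside the window, detection would have to come at least 36 - 4.3 = 31.7 weeks after conception under (a), or 36 - 18.3 = 17.7 weeks under (b). Table 1 schedules a pregnancy test at every two-weekly infusion visit, so detection that late is unlikely while infusions continue.

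The calculation takes birth as the time at which the outcome is known. An anomaly found before birth could fall inside (b) or (c), if someone were asking.

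**The case against.** The strongest objections are these.

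- **The shortest window is not the only one.** A reader might infer that a pregnant participant simply leaves the SAE window 30 days after confirmation. The documents do not settle this: sections 8.1 and 9 provide for longer follow-up. This stands. What can be said is that the rules conflict and that most birth outcomes fall outside the window whichever applies.
- **Section 9.3.4 limits start dates.** It also provides for follow-up to resolution or stabilization, and pregnancy is listed as an event of special interest. One could argue that a pregnancy must therefore be followed to its end. The protocol does not say so, and the discretion given in 9.3.8.2 points the other way. The argument is a reason to clarify the text.
- **Pregnancy loss.** A reader might infer that losses are missed too. A loss inside the window is already an AE under 9.3.1, and an SAE if it meets a listed criterion. The gap is clearest for malformation.
- **Reporting to the DSMB.** A reader might infer that no report would ever reach the board. That cannot be verified: Appendix 9 and the MOOP, to which reporting is partly delegated, were not available.
- **Partners of male participants.** Section 9 cautions men about contraception while MMF is received and states no rule for partner pregnancies. Following partners would add a newly consented group, and the documents give no risk figure for paternal exposure. It is a debatable extension and is not pressed here.
- **Prevention.** Pregnancy, planned pregnancy and lack of effective contraception are exclusions (6.2), testing is repeated, and study medication is stopped on suspicion. These measures make an exposed pregnancy unlikely. They do not ensure that its outcome is recorded.

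**Conclusion.** The gap is real and narrow. On the text available, a congenital malformation after MMF exposure could go unrecorded, because no SAE criterion names it, outcome follow-up is discretionary, and most births fall outside the recording window under each follow-up rule. The timing result rests on the gestation and detection assumptions above. The overall conclusion also assumes that Appendix 9 and the MOOP contain no stricter pregnancy rule.

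The expected effect on event counts is very small. There are 32 participants, few pregnancies are likely, and the documents give no pregnancy rate from which to compute an expected number. A reader might infer that the decision to proceed to a full-scale trial is at risk, since section 10.4.1 makes it subject to safety. The documents do not show that: the safety analysis is mainly descriptive (10.4.3), and no numeric safety threshold is attached to that decision. The case for change is that the harm is named and irreversible and the correction is cheap.

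**What to change.** 1. In section 9.3.2, add 'congenital anomaly or birth defect' to the list of serious outcomes.
2. In section 9.3.8.2, replace the PI's option with a requirement to follow every pregnancy in an exposed participant to its outcome, subject to her consent. Because allocation is blinded, apply this to anyone who has taken MMF or placebo.
3. In section 9.3.4, exempt that outcome from the 30-day limit.
4. Reconcile section 8.1, the Visit 17 reminder and Follow-up paragraph in section 9, and sections 9.3.4 and 9.3.8.2, so that the protocol states which follow-up rule governs a pregnant participant.

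If Appendix 9 or the MOOP already contains a suitable rule, cross-refer to it in 9.3.8.2 and make the protocol text agree with it. The cost is a wording amendment and a few extra contacts for each pregnancy that occurs. Sample size and efficacy analysis are unaffected.

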9.4 UNANTICIPATED PROBLEMS

9.4.1 DEFINITION OF UNANTICIPATED PROBLEMS (UP)

Unanticipated problems, in general, are defined as any incident, experience, or outcome that meets all of the following criteria:

- Unexpected (in terms of nature, severity, or frequency) given (a) the research procedures that are described in the protocol-related documents, such as the IRB-approved research protocol and informed consent document; and (b) the characteristics of the participant population being studied;
- Related or possibly related to participation in the research (in this guidance document, possibly related
 means there is a reasonable possibility that the incident, experience, or outcome may have been caused by
 the procedures involved in the research); and
- Suggests that the research places participants or others at a greater risk of harm (including physical, psychological, economic, or social harm) than was previously known or recognized.

9.4.2 UNANTICIPATED PROBLEM REPORTING

To ensure that appropriate steps are taken in a timely manner to protect other participants from avoidable harm, we will adhere to HHS regulations at 46.103(b)(5) and will promptly report unanticipated problems to the IRB, NIAMS, FDA, appropriate institutional officials, any supporting department or agency head (or designee), and OHRP.

- Unanticipated problems that are serious adverse events should be reported to the IRB, NIAMS, FDA etc. within 24 hours of the investigator becoming aware of the event.
- Any other unanticipated problem should be reported to the IRB, NIAMS, FDA etc. within 10 business days of the investigator becoming aware of the problem.

9.4.3 REPORTING UNANTICIPATED PROBLEMS TO PARTICIPANTS

Participants will be informed about unanticipated problems, and study-related results on an individual or aggregate level.

10 STATISTICAL CONSIDERATIONS

10.1 STATISTICAL HYPOTHESES

Primary Efficacy Endpoint(s):

Assess the feasibility of a short course of immune modulating therapy with daily mycophenolate mofetil (MMF). We will start to test the hypothesis that MMF for 12 weeks will safely attenuate immunogenicity conferred by pegloticase as determined by the proportion of participants achieving and maintaining a serum urate ≤ to 6 mg/dL through 12 weeks, compared to concurrent controls. After 12 weeks of co-administration, all participants will continue on pegloticase for an additional 12 weeks without combination MMF therapy to evaluate the durability and safety of this approach

Primary Safety Endpoint(s):

Assess the incidence and types of adverse events /infusion reactions.

Secondary Endpoints:

1) Determine the 6 month durability of immune modulation after discontinuation of the short course of MMF by: a) assessing the absolute change in serum urate from baseline to Week 24, and Week 12 to Week 24, and b) determining the proportion of participants with serum urate ≤ 6 mg/dL through 24 weeks, and Week 12 to Week 24; 2) Identify and characterize the pegloticase immune response by immunoglobulin isotypes (IgG and IgM), specificities, and antibody titer, and 3) Examine patient reported outcomes (PROs) using the National institute of Health (NIH) supported Patient Reported Outcomes Measurement Information System (PROMIS) and Gout Impact Scale (GIS) instruments.

10.2 SAMPLE SIZE DETERMINATION

As a pilot proof of concept study, we are not able to fully power the trial to detect a difference between a rate of 60% success vs the success rate after induction by MMF, which we hypothesize will be 80% or more. If we powered the study with 80% power, 2 sided type I error of 5%, we would require 82 participants per group to demonstrate this difference with a treatment and control group. To ensure resources are not wasted, we will confirm that a future larger study is worth pursuing based on results of this pilot study. We have included a decision table based on Fisher's exact tests to define how results will inform our decision about a future full scale study (see section 10.4.1).

